Consent will be obtained at least a day before surgery. Patients will be randomized the day of surgery upon presentation to the operating room to either a *treatment group* (PECS/SAP blocks) or a *control group* (standard parenteral analgesia technique with or without incisional LA infiltration) using secure web-based randomization. Randomization will be stratified by aortic or mitral valve surgery, with random blocking in each case. The system will be accessed shortly

before surgery to conceal allocation as long as possible. Clinicians will not be blinded to the intervention, but all outcomes will be assessed by research personnel who are blinded to the group assignment.

Anesthetic and Surgical Management

Anesthetic care will be performed as usual for Cleveland Clinic cardiothoracic surgical procedures. This includes use of standard ASA monitors and may include the use of arterial or central venous pressure monitoring, trans-esophageal echocardiography, and lung isolation using a bronchial blocker or a double lumen endotracheal tube. Medication administration for induction and maintenance of anesthesia will also be consistent with usual care and will include intravenous opioids such as fentanyl and hydromorphone. Intravenous lidocaine will not be administered upon induction of anesthesia.

Pressure-control ventilation will be used with a tidal volume not exceeding 6-10 ml/kg ideal body weight during two- and one-lung ventilation. Fluids will be managed conservatively per routine. Patients not extubated at the end of the procedure will be sedated with propofol. Surgical procedures with the assistance of the cardio-pulmonary bypass will be performed in their usual manner. The general approach for the AV replacement will be via the right anterior thoracotomy in the 3rd intercostal space.⁴ The MV repair/replacement procedures will be approached via the right lateral thoracotomy inframammary incision in the 4th intercostal space in the mid-axillary line and augmented, as needed, with the stab incisions for the robotic ports.⁴

Chest Wall Analgesia

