Liposomal bupivacaine dosing is not weight-based and the full 266-mg bottle can be administered to adult thoracic patients. A maximum of 150 mg bupivacaine HCL can be mixed with Exparel. This equates to one 30-mL bottle of 0.5% bupivacaine HCL or two (2) bottles of 0.25% bupivacaine HCL. If a higher volume of the local anesthetic is needed a 10 ml of normal saline can be added to the mixture of bupivacaine HCL and liposomal bupivacaine. Thus patients ≥ 60 kg will receive 150 mg of bupivacaine HCL, while patients weighing < 60 kg need to have the bupivacaine dose calculated but can still receive full 20 ml of Exparel.

Patients randomized to standard analgesia technique will be given parenteral opioids (such as fentanyl or hydromorphone) until they are converted to the enteral medications such as Percocet.

Study Measurements

Patent demographics will be collected from preoperative interviews and chart review (Table 1). Cumulative opioid consumption, non-opioid analgesics, and length of stay will be

captured electronically using Epic and/or PHDS. Other secondary and descriptive outcome data as well as surgical and intraoperative data will be collected prospectively (Table 2).

Data will be obtained from the following sources: The Society of Thoracic Surgeons (STS) database, Cardiovascular Information Registry (CVIR) of the Heart and Vascular Center at the Cleveland Clinic, the electronic medical record (EPIC), and the electronic Anesthesia Record Keeping System (ARKS).

a) OBAS score

The OBAS score questionnaire (Table 3) will be obtained and score calculated by the research team on post-operative days 1-3. We will calculate the average of the OBAS scores obtained. The OBAS score is a validated postoperatively calculated, multi-dimensional questionnaire that consists of 7 items (Table 3) encompassing not only scale-rated pain score but different aspects of analgesia benefits, side effects and overall patient's satisfaction.⁵³

The OBAS score is based on 7 questions and ranges from 0 to 28 points that will be administered on POD 1 – POD 3. Although these are longitudinal ordinal data, we will be able to treat OBAS scores as continuous data in the analyses with the lower score correlating with better resolution of the analgesia treatment. A 20% reduction in OBAS geometric mean, a-priori, was defined as minimal clinically important difference..^{57,58}

b) Pain assessments

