The Blood samples will be collected into K2EDTA tubes and will be centrifuged at 1000 to 1200g for 10 min to obtain plasma within 1 hour of collection. After centrifugation, the plasma will be transferred into polypropylene tubes. The plasma samples will be stored frozen at -20°C or colder until shipment. All samples will be shipped frozen with dry ice to ABS Laboratories, Inc. The shipment address is as follows: [name] ABS Laboratories, Ltd. [name]

Descriptive and Safety Outcomes

- a) Total ICU length of stay;
- b) Hospital length of stay;
- c) Cumulative non-opioid analgesics included acetaminophen, ketorolac, ibuprofen, gabapentin, and pregabalin will be recorded and compared over the initial three postoperative days;
- d) Anxiolytics such as alprazolam, lorazepam, and diazepam will be recorded and compared.

Statistical analysis

We will compare groups on potentially confounding demographic and preoperative risk factors listed in Table 1 using appropriate summary statistics (i.e., mean ± standard deviation, median [Q1, Q3], or N (%) as appropriate) as well as surgical and intraoperative data will be collected prospectively (Table 2). Randomized groups will be compared on balance on these characteristics using absolute standardized difference, defined as the absolute difference in means, mean ranks, or proportions divided by the pooled standard deviation.

Analyses will be modified intent-to-treat, including all randomized patients who received PECSII/serratus blocks (regardless of whether it's consistent with the randomization).

We will summarize descriptive and safety outcomes by randomized groups using appropriate summary statistics (i.e., mean \pm standard deviation, median [Q1, Q3], or N (%) as appropriate). No statistical tests will be performed on these outcomes.

We will use an alpha of 0.05 for both the primary and secondary analyses, with a significance criterion of 0.05 for the primary analysis and 0.0167 for each secondary analysis (i.e., 0.05/3, Bonferroni correction). Analyses will be completed using SAS version 9.4 or newer (SAS Institute, Carey, North Carolina) or R version 3.2.4 or newer (R Project for Statistical Computing, Vienna, Austria).

Primary analysis

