We will estimate the PECS/SAP blocks effect on OBAS scores using a repeated measures linear regression model with an autoregressive correlation structure, adjusting for ALL imbalanced confounders (if any). Based on these model we would be able to claim if the PECS/SAP blocks had any effect on the OBAS score compared to standard routine analgesia during any of the postoperative time up to third postoperative day. Due to non-normality of OBAS score, it will be log-transformed for analysis. We will report model based P-value and the geometric mean ratio for OBAS scores along with confidence intervals. To assess whether the PECS/SAP blocks effect is heterogeneous over three postop days, we will assess the treatment-by-time interaction using a significance criterion of 0.20. If it appears that the treatment effect is heterogeneous, we will report the treatment effect separately for each postoperative day POD 1, POD 2 and POD 3 using a Bonferroni correction as appropriate (e.g., 0.05/3; 3 postoperative days).

Secondary Analysis

Morphine equivalents will be calculated based on the conversions specified in Table 4 below. Total opioid consumption as well as intraoperative and postoperative day 1, 2, and 3 totals will be collected and converted to milligram morphine equivalents. Patients will not be provided opioid patches for pain relief because there is no known conversion to morphine equivalents. Cumulative opioid consumption data is typically right skewed, so we will normalize it for analyses using a log transformation. Opioid consumption will be reported separately for postoperative day (POD) 0 after surgery, POD 1, POD2, and POD3. We will estimate the effect of PECS/SAP blocks to standard routine analgesia on log cumulative opioid consumption using a repeated measures linear regression model with an autoregressive correlation structure, adjusting for any imbalanced baseline or surgical characteristics between groups.

To assess whether the effect of PECS/SAP blocks is heterogeneous over time, we will assess the treatment-by-time interaction using a significance criterion of 0.20. If it appears that the treatment effect is heterogeneous, we will report the treatment effect separately for each postoperative day using a Bonferroni correction as appropriate (e.g., 0.05/3; 3 postoperative days).

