We also plan for two interim analyses at 1/3 and 2/3 of the planned enrollment to assess safety, feasibility and formal efficacy and futility. Therefore, interim adjusted sample size is N=98 patients per group, or N=196 total. We will use the conservative gamma spending function with parameters -5 and -5 for alpha (efficacy) and beta (futility), respectively. If the alternative hypothesis is true (the treatment effect exists) there will be a cumulative probability of 10%, 53% and 100% of crossing either an efficacy or futility boundary at the 1st, 2d and final analyses, respectively (Table A and Figure 1 below contains boundary Information). Planned first and second interim analyses will be performed upon accrual of 66 and 132 patients respectively. **Therefore, planned number of patients for the analysis is N=98 patients per group, or N=196 total.**

We will also enroll at least 5 pilot patients in the beginning of the study to test the feasibility of protocol adherence and data collection.

Table A. Boundary Information for interim analysis (3 analyses = 3 stages):

Boundary Information (Standardized Z Scale)**Null Reference = 0**

Stage	Information Level	Alternative		Boundary Values				
		Reference	Lower	Lower	Upper	Beta	Beta	
	Proportion	Lower	Upper	Alpha	Beta	Beta	Alpha	
1		0.3333	-1.88730	1.88730	-3.18319	-0.02167	0.02167	3.18319
2		0.6667	-2.66904	2.66904	-2.64022	-0.53609	0.53609	2.64022
3		1.0000	-3.26890	3.26890	-1.97517	-1.97517	1.97517	1.97517

Figure 1. Boundary plot

[figure not shown]

Table 1: Patient demographic and preoperative risk factors

Sex
Age (years)
Surgery Type (Robot MVR, thoracotomy MVR, AVR through RAT)
Coronary Artery Disease
Hypertension
Pervious Myocardial infarction
Peripheral Arterial Disease
Previous vascular surgery
Smoker (current or former)
Cerebrovascular disease
Diabetes mellitus

Renal failure: Indicate whether the patient has 1) a documented history of renal failure and/or 2) a history of creatinine > 2.0. Prior renal transplant patients are not included as pre-op renal failure unless since transplantation their creatinine has been or currently is > 2.0.
Left ventricular EF

Table 2: Surgical, intraoperative and postoperative data

Time on CPB
X-clamp time
RBCs
Plt
FFP
Cryo
Inotropes in the OR
Time to extubation
Length of ICU stay
Length of hospital stay

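### The only analysis-set rule admits only patients who received the block; read literally it excludes unblocked controls and contradicts the planned comparison and the 98 per group

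*Combined protocol and SAP*

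**What the plan says.** The combined protocol and SAP has one analysis-set rule, in the Statistical analysis section: "Analyses will be modified intent-to-treat, including all randomized patients who received PECSII/serratus blocks (regardless of whether it's consistent with the randomization". Receipt of the block is the condition for entry.

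The control arm is not given that block. The Study protocol section describes it as "standard parenteral analgesia technique with or without incisional LA infiltration", and the end of the Local anesthetic section says "Patients randomized to standard analgesia technique will be given parenteral opioids", followed by enteral medication.

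The analyses need both arms. The Primary analysis section asks whether "the PECS/SAP blocks had any effect on the OBAS score compared to standard routine analgesia". The Secondary Analysis section says "We will estimate the effect of PECS/SAP blocks to standard routine analgesia on log cumulative opioid consumption". Sample Size Considerations states that the "planned number of patients for the analysis is N=98 patients per group, or N=196 total", and plans two interim analyses "to assess safety, feasibility and formal efficacy and futility".

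On grouping, the Statistical analysis section says "Randomized groups will be compared on balance on these characteristics using absolute standardized difference", and descriptive and safety outcomes are also summarized by randomized group. The primary and secondary model descriptions do not say whether patients are grouped as randomized or as treated. The exploratory models refer only to two groups.

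**The concern.** An analysis set must contain both arms of the comparison it serves. This one is defined by receipt of the experimental treatment, so it keeps the block arm and any control who crossed over, and drops the other controls. The primary population therefore cannot be built from the text, and whoever programs the analysis has to supply a rule.

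Several repairs are plausible, and they are not equivalent:

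- all randomized patients, grouped as randomized;
- patients who received either study treatment, grouped as randomized;
- all patients, grouped by the treatment they received;
- all controls, with unblocked block-arm patients dropped.

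The third and fourth let an event after randomization decide who is counted, or in which group. Clinicians are not blinded (Study protocol section), so that event could be related to prognosis. The choice should be fixed in writing, not left to the analyst.

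**Working it through.** **Text set side by side**

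1. Entry rule (Statistical analysis): the patient was randomized and received the PECS II/serratus block.
2. Control treatment (Study protocol; Local anesthetic): standard analgesia, no PECS II/serratus block.
3. From 1 and 2, a control enters only by crossing over. With no crossovers the set is 98 + 0 and the block effect cannot be estimated. With crossovers, everyone in the set has been blocked, so there is still no comparison with standard analgesia.
4. The Primary analysis, the opioid analysis and the figure of 98 per group all require unblocked controls. No other sentence brings them back in.

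**The planned size presupposes two full arms**

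Inputs from Sample Size Considerations: CV 50%, geometric mean ratio 0.80, alpha 0.05 (taken as two-sided; Table A's boundaries are symmetric), power 90%.

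- Log-scale SD = sqrt(ln(1 + 0.5²)) = 0.4724; effect = |ln 0.80| = 0.2231.
- n per group = 2 × (1.960 + 1.2816)² × 0.4724² / 0.2231² = 94.2, so 95 by the normal approximation and 96 with the noncentral t. The plan states 96.
- Interim inflation from Table A's final reference value = (3.26890 / 3.2415)² = 1.0170; 192 × 1.0170 = 195.3, rounded up to 196. The plan states 196, or 98 per group.

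The stated sizes reproduce, but only with a full control arm.

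**Cost of analysing everyone as randomized**

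The documents give no rate at which assigned blocks are not performed, so 2%, 5% and 10% are assumed, with no effect in unblocked patients. If a share p of the block arm is unblocked, the log effect becomes ln(0.80) × (1 − p), and Table A's final reference value becomes 3.2689 × (1 − p). Power was simulated with Table A's efficacy and futility boundaries at information 1/3, 2/3 and 1, treating the outcome as a single averaged normal variable and following the futility boundary. At p = 0 the simulation gives cumulative crossing probabilities of 10%, 53% and 100%, which match the plan.

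| Not blocked (assumed) | Diluted ratio | Final reference value | Power with Table A | Fixed design, 98 per arm |
|---|---|---|---|---|
| 0% | 0.800 | 3.269 | 90.0% | 91.1% |
| 2% | 0.804 | 3.204 | 88.8% | 90.0% |
| 5% | 0.809 | 3.105 | 86.9% | 88.1% |
| 10% | 0.818 | 2.942 | 83.1% | 84.5% |

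The fixed-design column is slightly optimistic, because it ignores the interim looks that the 98 already allows for. The Table A column is the one to use.

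**The case against.** The strongest reply is that this is a drafting slip which the rest of the text resolves. The plan compares the block with standard analgesia and counts 98 analysed patients in each group, so no reader would really drop the controls. That is fair as to intent. A reader might infer that the trial plans to analyse blocked patients only, and the documents do not support that. But evident intent does not supply the missing rule: the one rule stated still gives the wrong set.

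On grouping, the reply has more force. The label points to as-randomized analysis. Imbalance is measured between randomized groups, and the primary model then adjusts for the imbalanced variables, which suggests the same groups. The parenthesis may mean that patients whose treatment departed from allocation are kept. A reader might infer that the plan adopts an as-treated analysis; the text does not establish that. What stands is that the grouping is not stated and that the parenthesis allows either reading.

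A reader might also infer an inflated type I error, on the view that controls would be kept and unblocked block-arm patients dropped. The plan does not state that rule. Any error rate would rest on an assumed non-receipt rate and an assumed difference in prognosis. The Chest Wall Analgesia section also lets the block be done at the end of surgery if it cannot be done beforehand, which should keep non-receipt low. No such figure is relied on here.

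Lastly, the interim text gives accrual counts (66 and 132) and names no analysis set. That the same rule governs those looks is a reasonable inference from its being the only one, not something the plan says.

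**Conclusion.** Wrong as written, and to be corrected before analysis. The sole analysis-set rule excludes all controls who did not receive a block, against 98 controls planned for analysis. This follows from the text alone and needs no assumption. It measures a contradiction in the drafting, not what is likely to be run.

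The grouping point is weaker. As-randomized grouping is the better reading, but the efficacy models do not state it. The documents do not show that controls will be dropped, that an as-treated analysis is intended, or that the type I error is inflated by any particular amount. The power figures describe only the cost of the remedy, and they rest on assumed non-receipt rates and on no effect in unblocked patients.

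**What to change.** Replace the sentence with: *The primary and secondary analyses include all randomized patients with outcome data, in the group to which they were randomized, whether or not a block was given.* Make analysis by block received a sensitivity analysis only, and state that the interim analyses use the same primary set.

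Deal with conversions to sternotomy explicitly. The Version 4 change summary records 12 patients converted during surgery, after randomization, who were regarded as not qualified and whose follow-up could not be completed. The present rule does not exclude a converted patient who had already been blocked, and blocks are normally placed before incision. If such patients are left out, state this as an exception to intention-to-treat and justify it; restricting the set to patients who had the planned surgery would itself select on an event after randomization. Report by arm the 12 conversions and any other randomized patients not analysed.

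The cost is one sentence of wording and a by-arm count. Planned N need not change. If some assigned blocks are not given, the dilution costs about 1.2, 3.1 and 6.9 points of power at the assumed 2%, 5% and 10% (90.0% less 88.8%, 86.9% and 83.1%).

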PECS/SAP blocks with liposomal bupivacaine improve the Overall Benefit Analgesia Score averaged over the postoperative days 1, 2, and 3. A 20% reduction in OBAS geometric mean, a-priori, was defined as minimal clinically important difference.

Secondary hypotheses:

- (1) PECS/SAP blocks decrease postoperative cumulative opioid consumption over the initial three postoperative days.
- (2) PECS/SAP blocks improve pulmonary mechanics, on each of the postoperative days 1, 2 and 3, from the baseline.

Exploratory Hypothesis:

- (1) PECS/SAP blocks improve the Quality-of-Recovery score averaged over the postoperative days 1 and 3, with a difference of 8 points being considered the minimum clinically important difference.⁵⁴
- (2) PECSII and SAP blocks reduce persistent postoperative surgical pain

Methods

The study will be conducted at the Cleveland Clinic Main Campus with IRB approval and written informed consent from participating patients.

Inclusion Criteria

1. 18-85 years old;
2. Elective MICS for isolated robotically-assisted mitral valve repair via anterolateral thoracotomy approach.

Exclusion Criteria

1. Weight less than 50 kg;
2. Pregnancy or lactation;
3. Emergency surgery and patients transferred from the ICU to the operating room;
4. Redo cardiothoracic surgery or post-operative reoperation within 72 hours of index procedure (including minor chest wall procedures including tube thoracostomy, thoracentesis or percutaneous drain placement);
5. Anticipated endotracheal intubation > 24 hours;
6. Anticipated non-study nerve block that provides analgesia to the intercostal nerves;
7. Active systemic or cardiopulmonary infection;
8. Mechanical circulatory support;
9. Allergy or contraindication to study local anesthetics;
10. Current chronic pain or routine opioid use (patients on chronic enteral opioids like Percocet or Vicodin) in a dose of > 30 mg of morphine-milligram-equivalents for at least 10 days in last 30 days;
11. Poorly controlled psychiatric disorders;
12. Clinically important current neurologic deficit; e.g. spinal cord injury, paralysis of extremity, any neurologic deficit in the region of the block
13. Active liver disease or cirrhosis;
14. Pacemaker generator or breast implants ipsilateral to surgery;
15. Previous participation in this study.
16. eGFR <30 or chronic kidney disease

Study protocol

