We will estimate the effect of PECS/SAP blocks on FEV_1 , FVC and peak flow rate using three separate repeated measures regression models with an autoregressive correlation structure, adjusting for baseline FEV_1 , FVC, peak flow rate and imbalanced confounders (if any).

The Wald tests for regression model coefficients will be used to test each of the secondary hypotheses; the Bonferroni correction for four outcomes will be employed to control the overall Type I error rate at 0.05 for the secondary outcomes.

Exploratory Analysis

Two separate linear regression models will be developed to assess the relationship between analgesia strategy and each of the two exploratory outcomes (quality of recovery after anesthesia survey and persistent postoperative surgical pain). To compare patients from two groups on these outcomes mean difference will be reported along with 95% confidence intervals.

Descriptive and Safety Analyses

We will summarize descriptive and safety outcomes by randomized groups using appropriate summary statistics (i.e., mean \pm standard deviation, median [Q1, Q3], or N (%) as appropriate). No statistical tests will be performed on these outcomes.

Sample Size Considerations

Per Mamoun, observed a coefficient of variation (CV) of 53% in the placebo group of cardiac surgery patients.⁵⁹ We assumed a slightly more conservative CV of 50% and that the treatment effect favored PECS/SAP blocks by 20% (i.e., true ratio of geometric means of 0.80). We will need to enroll approximately 192 patients (96 per group) to have 90% power at the 0.05 significance level to detect superiority of PECS/SAP blocks to standard routine parenteral and enteral analgesia in patients recovering from MICS .

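### The per-test threshold for secondary analyses (0.05/3 = 0.0167) contradicts the plan's own four-outcome Bonferroni correction, which gives 0.05/4 = 0.0125

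*Combined protocol and SAP*

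**What the plan says.** The Statistical analysis section assigns an overall alpha of 0.05 to the secondary analyses as well as to the primary one. It then sets the per-test criteria: "with a significance criterion of 0.05 for the primary analysis and 0.0167 for each secondary analysis (i.e., 0.05/3, Bonferroni correction").

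The Secondary Analysis section describes the tests themselves. For opioids: "We will estimate the effect of PECS/SAP blocks to standard routine analgesia on log cumulative opioid consumption using a repeated measures linear regression model". For FEV1, FVC and peak flow it specifies "three separate repeated measures regression models with an autoregressive correlation structure". It closes with the multiplicity rule: "the Bonferroni correction for four outcomes will be employed to control the overall Type I error rate at 0.05 for the secondary outcomes". It does not print the resulting per-test threshold.

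Two secondary hypotheses are numbered under Secondary hypotheses: "PECS/SAP blocks decrease postoperative cumulative opioid consumption over the initial three postoperative days" and "PECS/SAP blocks improve pulmonary mechanics, on each of the postoperative days 1, 2 and 3, from the baseline". The Aims of the study section likewise numbers two secondary aims.

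**The concern.** Both sections apply a Bonferroni correction to the same family at the same overall level, but with different divisors. They cannot both be followed. Nothing in the current text counts three secondary analyses: there are two numbered aims, two numbered hypotheses, and four modelled outcomes.

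What is at stake is the decision rule for secondary claims. A p-value of, say, 0.015 for FVC would be declared significant by a reader of one section and not by a reader of the other. If the contradiction stands when the data are analysed, that choice can be made with the results in view. And if the looser threshold is used, the control of Type I error at 0.05 stated in the Secondary Analysis section is not guaranteed.

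**Working it through.** **Inputs from the documents**
- Overall secondary alpha: 0.05 (Statistical analysis; Secondary Analysis).
- Printed per-test threshold: 0.0167, given as 0.05/3 (Statistical analysis).
- Number of secondary outcomes: 1 opioid model + 3 spirometry models = 4 (Secondary Analysis), which is also the number named in that section's Bonferroni rule.

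**Step 1. Reproduce the printed figure.** Bonferroni threshold = alpha / k. With k = 3, 0.05/3 = 0.016667, which rounds to 0.0167. The division is correct; the divisor is the problem.

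**Step 2. Apply the plan's own counts.**
- k = 4 outcomes: 0.05/4 = 0.0125.
- k = 2 numbered hypotheses: 0.05/2 = 0.025.

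Neither gives 0.0167.

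**Step 3. Family error with four tests.**

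| Per-test level a | Bonferroni bound, 4a | If independent, 1 − (1 − a)^4 |
|---|---|---|
| 0.05/3 | 0.0667 | 0.0650 |
| 0.0125 | 0.0500 | 0.0491 |

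**Step 4. Allow for correlation.** The documents give no correlations, so this is an assumed range. Take the three spirometry z-statistics as equally correlated at r and the opioid statistic as independent of them. Then family error = 1 − (1 − a) × P(all three spirometry |Z| below the critical value), with two-sided critical values 2.394 (a = 0.05/3) and 2.498 (a = 0.0125).

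| r | at 0.05/3 | at 0.0125 |
|---|---|---|
| 0 | 6.5% | 4.9% |
| 0.5 | 6.0% | 4.6% |
| 0.8 | 5.1% | 3.9% |
| 0.83 | 5.0% (just under) | 3.8% |
| 0.9 | 4.6% | 3.5% |

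At 0.0167 the family error drops below 5% only from about r = 0.83. At 0.0125 it cannot exceed 5% whatever the correlation.

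**Step 5. How often the two rules disagree.** For one outcome with no effect, the chance that p falls between the thresholds is 0.0167 − 0.0125 = 0.0042.

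**Step 6. Power cost of the stricter threshold.** The documents state no secondary power, so the starting values are assumed. New power = Φ(z_power + 2.394 − 2.498):
- from 80%: Φ(0.8416 + 2.394 − 2.498) = 0.770
- from 90%: Φ(1.2816 + 2.394 − 2.498) = 0.881

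The differences, about 3.0 and 1.9 percentage points, are also the chances that the two rules disagree on an outcome with that power.

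**The case against.** The best defence is that the practical weight is low. The thresholds differ by 0.0042. Spirometry measures from the same patient may be strongly correlated, and with a high enough correlation 0.0167 would hold the family error at or below 5%. The Secondary Analysis section is also the more specific text: it names the tests, their number and the error rate to be held, so a statistician working from it would use 0.05/4 anyway. On that view 0.0167 is a leftover divisor and not a design flaw.

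Most of this stands as a statement about size. It does not remove the contradiction. The plan promises control by Bonferroni, which needs no correlation assumption, and it supplies no correlation to justify a looser rule. That the specific section points to four supports correcting the general one.

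A second defence is that 0.05/3 is really the correction for three postoperative days. The plan does use 0.05/3 for that purpose, but as a separate step that applies only if the treatment-by-time interaction suggests heterogeneity. The sentence at issue attaches 0.0167 to each secondary analysis without that condition.

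Nor is this a difference between the amendment log and the body. Both rules stand in the current text. The log records that QoR-15 moved to exploratory status, so it does not belong in the secondary count.

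**Conclusion.** The point holds: the 0.0167 criterion is wrong as written, because it divides by three where the plan has four secondary outcomes and says it corrects for four. The implied threshold is 0.0125. This rests on the documents alone and needs no outside figure. The effect is modest: a bound of 6.7% in place of 5%, and a band of p-values from 0.0125 to 0.0167 in which the two sections give opposite answers. Where the true family error lies under that bound depends on correlations that the documents do not give.

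Three stronger readings might be inferred and are not supported:
- *The secondary Type I error will exceed 5%.* It is not guaranteed to stay at 5%, which is different. A spirometry correlation above about 0.83, with opioid use independent, would keep it below.
- *The primary result or the sample size is compromised.* The primary analysis has its own criterion of 0.05, and the sample size is built on the primary outcome.
- *Day-by-day opioid tests must also fit within 0.0125.* The documents state no such rule. How the by-day tests and the day count are handled is a separate matter from the divisor.

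**What to change.** In the Statistical analysis section, replace 0.0167 with 0.0125 and 0.05/3 with 0.05/4, so that it agrees with the four-outcome rule in the Secondary Analysis section. Make the change before secondary results are interpreted.

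The edit is one number and its divisor. The statistical cost is the small power loss shown above for secondary outcomes (80% to 77.0%, or 90% to 88.1%, from assumed starting values). No model, primary criterion or enrolment figure changes.

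### The primary test has two final thresholds: a 0.05 criterion in the analysis section and |Z| = 1.97517 (p = 0.0482) in the stopping plan, and nothing says which governs

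*Combined protocol and SAP*

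**What the plan says.** The Statistical analysis section opens its error-rate paragraph with "We will use an alpha of 0.05 for both the primary and secondary analyses". In the same sentence it then sets a threshold per test: "with a significance criterion of 0.05 for the primary analysis", and 0.0167 for each secondary analysis. It does not mention interim looks. The Primary analysis section promises a model-based p-value and a geometric mean ratio with confidence intervals, and gives no interim-adjusted level for either.

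Sample Size Considerations sizes the trial "to have 90% power at the 0.05 significance level to detect superiority". It then adds two interim analyses, at one third and two thirds of enrolment (66 and 132 patients), for efficacy and futility among other purposes: "We will use the conservative gamma spending function with parameters -5 and -5 for alpha (efficacy) and beta (futility), respectively". Table A gives these values on the Z scale:

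| Stage | Efficacy boundary, absolute Z | Futility boundary, absolute Z |
|---|---|---|
| 1 | 3.18319 | 0.02167 |
| 2 | 2.64022 | 0.53609 |
| 3 (final) | 1.97517 | 1.97517 |

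No section says that the Table A final boundary replaces the 0.05 criterion, or whether the futility boundaries are binding.

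**The concern.** Once alpha has been spent at two efficacy looks, the full 0.05 is no longer available as a nominal threshold at the end. An analyst working from the Statistical analysis section would compare the final p-value with 0.05. One working from Table A would compare |Z| with 1.97517. For a result in the narrow band between the two, the primary conclusion depends on which section is followed, and that choice would be made with the result in view.

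A second, smaller matter is linked to it. Whether 1.97517 itself holds 5% depends on what happens after a futility crossing, and the text leaves this unsaid.

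**Working it through.** **Inputs.** From the Statistical analysis section: criterion 0.05, that is |Z| ≥ 1.95996 two-sided. From Sample Size Considerations and Table A: gamma(-5) spending for alpha and beta, information 1/3, 2/3 and 1, the boundaries above, drift 3.26890 at full information, 90% power, N of 192 raised to 196. Two-sided 0.05 is inferred from the symmetric boundaries in Table A and confirmed by step 1. Z statistics are treated as normal with independent increments.

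**1. Reproduce Table A.** Cumulative alpha is α(t) = 0.05 × (1 − e^(5t)) / (1 − e^5).
- t = 1/3: 0.05 × 4.2945 / 147.413 = 0.00146
- t = 2/3: 0.05 × 27.032 / 147.413 = 0.00917
- t = 1: 0.05

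The first boundary solves 2(1 − Φ(z)) = 0.00146, so z = 3.18319. The other two come from recursive numerical integration.

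| | Stage 2 | Final |
|---|---|---|
| Table A | 2.64022 | 1.97517 |
| Recomputed, futility stops enforced | 2.64021 | 1.97518 |
| Recomputed, futility ignored | 2.64034 | 1.98335 |

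Table A is therefore a binding-futility design. With its boundaries, cumulative alpha is 0.00146, 0.00917 and 0.05000. At drift 3.26890, power is 0.9000 and the cumulative stopping probability is 10.0%, 53.4% and 100%, against the stated 10%, 53% and 100%. The inflation factor (3.26890/3.24152)² = 1.0170 gives 192 × 1.0170 = 195.3, consistent with 196.

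**2. Nominal level of the final boundary.** 2(1 − Φ(1.97517)) = 0.04825. The two rules disagree for p between 0.04825 and 0.05.

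**3. Overall two-sided type I error**, with the Table A efficacy boundaries at both looks:

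| Final criterion | Futility stops enforced | Futility not enforced |
|---|---|---|
| Z of 1.97517 (Table A) | 5.00% | 5.09% |
| Z of 1.95996 (p < 0.05) | 5.16% | 5.26% |

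The largest excess is 5.26 − 5.00 = 0.26 percentage points. With futility not enforced, a final boundary of 1.9834 (p = 0.0473) restores 5.0%.

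**4. How often the band matters.** With futility stops enforced, the probability of reaching the final analysis with |Z| between 1.960 and 1.975 is 0.16% under the null, 0.24% at the design effect and 0.53% at half the design effect.

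**5. Dependence on timing.** The value 1.97517 is exact only at 1/3 and 2/3. Of 196 patients, 66 and 132 are 0.337 and 0.673. The Version 5 change note raises total enrolment to about 214, although the sample size section keeps 196 for analysis. As an assumption, suppose all enrolled patients were analysed, with looks at 66 and 132 and Table A's futility values held. Gamma(-5) spending then gives these final boundaries:

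| Patients analysed | Final boundary |
|---|---|
| 196 | 1.976 |
| 208 | 1.970 |
| 214 | 1.966 (p about 0.0493) |

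**The case against.** The best defence is that the 0.05 in the Statistical analysis section divides alpha among outcomes, not among looks. On that view the section gives the total, Sample Size Considerations spends it, Table A preserves 5.00%, and only a cross-reference is missing. This is coherent and shows that the wording is ambiguous. It does not remove the conflict. The sentence names the overall alpha first and then pairs the 0.05 criterion with 0.0167, which is plainly a per-test threshold. No section says that Table A takes precedence.

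Three parts of the defence stand. The excess is small, and step 4 shows that the band would rarely be hit. No section permits a futility crossing to be overridden. A fixed threshold of 0.0482 would itself depart from the spending function if the information fractions differ from 1/3 and 2/3.

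A reader might infer more than the documents support:
- **Uncontrolled looks.** Testing at 0.05 at all three analyses would give about 10.6%, but the plan does not propose this. The interim boundaries are pre-specified and strict.
- **Expected overrides.** Under the null, 1.7% + 39.9% = 41.6% of trials cross a futility boundary at one of the two looks, so it is tempting to treat overrides as likely. Silence is not permission, and overriding every crossing would cost only 0.09 points under Table A.

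**Conclusion.** The point holds as a conflict in the primary decision rule, with a small numerical consequence. Followed literally, the 0.05 criterion gives an overall type I error of about 5.16% with futility stops enforced, or 5.26% without, against the intended 5.0%. Table A is correct for the design it describes: looks at exactly 1/3 and 2/3, and a stop at every futility crossing. The sample size and stated power are not in question. These figures rest on the normal approximation and on the looks taking place as planned. The matter should be settled before the final analysis because it is inexpensive to correct and should not be open to choice once a p-value is known.

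**What to change.** - **Statistical analysis:** state that 0.05 is the overall two-sided alpha for the primary outcome, and that the primary test at each stage is judged against the gamma(-5) spending-function boundary. Cite Table A (final |Z| ≥ 1.97517, p < 0.0482, at information 1/3, 2/3 and 1), and say that the boundaries are recomputed if the actual information fractions differ.
- **Primary analysis:** report the final confidence interval at the matching level. With Table A as printed this is 1 − 0.04825, about 95.2%.
- **Sample Size Considerations:** state that Table A was computed with binding futility. If a crossing may be overridden, use the non-binding final boundary (about 1.983, p about 0.0473), because 1.97517 would then give about 5.09%.

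The cost is a few sentences and a final threshold slightly stricter than 0.05. Under binding futility the stated 90% power is unchanged, since it was computed with the Table A boundary. The non-binding option raises the final boundary by a further 1.983 − 1.975 = 0.008 on the Z scale.
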